8.2.6.2 Analysis of Continuous Variables

Continuous secondary endpoints will be presented as per Section **Error! Reference source not found..** The continuous secondary endpoints are:

- DAS28-4 ESR
- DAS28-4 CRP
- TJC
- SJC
- Duration of morning stiffness
- EuroQoL EQ-5D-3L
- SF-12v2 Questionnaire (PCS_{SF12}, MCS and 8 health domains)
- FACIT-Fatigue Questionnaire
- Pain

8.2.6.3 Analysis of Categorical Variables

Categorical secondary endpoints will be presented as per Section 8.1.5. The categorical secondary endpoints are:

- DAS28 (EULAR Criteria)
- GIRERD Questionnaire

8.2.6.4 Analysis of Binary Variables

Binary secondary endpoints will be presented as per Section **Error! Reference source not found..** The binary secondary endpoints are:

- LDA
- Patients in remission
- FiRST Questionnaire

8.2.6.5 Further Analyses

Summaries will be produced for SDAI, CDAI, PhGA, PtGA, with summarises as per Section **Error! Reference source not found.**. The ACR-EULAR 2011 Boolean criteria will be summarised as per Section **Error! Reference source not found.**.

The association between baseline PCS total score (<20 vs ≥ 20) and baseline characteristics will be explored using univariate and multivariate logistic regressions. Baseline characteristics are listed hereafter:

- Sex (Female/Male)
- Age (years)
- BMI (kg/m²)
- Time between initial diagnosis of rheumatoid arthritis and inclusion (years)
- Number of painful joints
- Number of swollen joints
- Evaluation of pain (mm)
- Erosions (No/Yes)
- RF (-/+)
- ACPA (-/+)
- CRP (mg/ml)
- ESR (mm/hour)
- DAS28-4 CRP
- DAS28-4 ESR
- FACIT-Fatigue
- SF-12 Physical Component Summary
- SF-12 Mental Component Summary
- EuroQoL EQ-5D-3L
- Established diagnosis of a depressive syndrome (No/Yes)
- Previously treated by csDMARD (No/Yes)
- Previously treated by biological treatments or tsDMARD (No/Yes)
- Number of previous biological treatments or tsDMARD by patient
- Concomitant conventional synthetic DMARD (No/Yes)

8.2.7 Subgroup Analyses

All efficacy variables, TEAEs and AEs of interest (Herpes Zoster and Serious Infections) will be described by sex and patient age (< 65 years, ≥ 65 years).

8.2.8 Impact of Covid-19 on study results

The impact of Covid-19 (if any) on the study results will be assessed. The number of delayed/missing visits during the lockdown period in France (from the 17th march 2020 to the 10th may 2020) will be provided.

8.2.9 Summary of Analyses

Table 8 Summary of Main Analyses

Outcome	Analysis Set	Supports Protocol Objective Number	Subgroups	Statistical Method	Covariates/ Strata	Missing Data
Time to discontinuation of Tofacitinib	Full Analysis Set (FAS)	1	None	Cox PH model	Univariate model selection, followed by backwards selection on the variables in Figure 2 .	Missing data indicators
Sensitivity Analysis – Only to be used in the event of >10% missing data: Time to discontinuation of Tofacitinib	FAS	1 – Sensitivity Analysis	None	Cox PH model	Univariate model selection, followed by backwards selection on the variables in Figure 2 .	Complete Case Analysis
Sensitivity Analysis: Time to discontinuation of Tofacitinib	FAS	1 – Sensitivity Analysis	None	Random Survival Forests	Variables in Figure 2 , following methods seen in Section 8.1.1.2 Random Survival Forests .	Random Survival Forests missing data algorithm.
Sensitivity Analysis: Time to discontinuation of Tofacitinib	Month 3 Analysis Set	1 – Sensitivity Analysis	None	Cox PH model	Univariate model selection, followed by backwards selection on the variables in Figure 2 and Das28-4 CRP at Baseline.	Missing data indicators
Sensitivity Analysis: Time to discontinuation of Tofacitinib	Month 3 Analysis Set	1 – Sensitivity Analysis	None	Random Survival Forests	Variables in Figure 2 and DAS28-4 CRP at Month 3, following the methods seen in Section 8.1.1.2 Random Survival Forests .	Random Survival Forests missing data algorithm.
Time to discontinuation of Tofacitinib	FAS	2	None	Cox PH model	Baseline CSQ and baseline PCS	No missing data methods used.
Time to discontinuation of Tofacitinib	FAS	2	None	Cox PH model	Last recorded CSQ and PCS before discontinuation.	No missing data methods used.
Time to discontinuation of Tofacitinib	FAS	2	None	Cox PH model	Change from baseline to last recorded CSQ and PCS before discontinuation.	No missing data methods used.

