5.3 MONTH 3 ANALYSIS SET

The Month 3 Analysis Set will include patients who receive at least one dose of Tofacitinib, have at least one set of post-baseline measurements and who have at least one non-missing month 3 measurement.

The sensitivity analyses where DAS28-4 CRP measured at month 3 is included as a potential factor will use the Month 3 analysis set.

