8.2.4 Sensitivity Analyses

Sensitivity analyses, except where specified, will use the FAS. All sensitivity analyses tables will present a single Tofacitinib Total column, using the treatment label seen in Section 2.3. All sensitivity analyses plots will present Tofacitinib as Monotherapy and Tofacitinib as Combination, using the treatment labels seen in Section 2.3.

Complete Case Analysis

In the event of more than 10% missing data in baseline covariates then a complete case analysis will take place, using the methods described in Section 7.2.

Random Survival Forests

Random survival forests will be created as a sensitivity analysis to complement the standard Cox PH model, as described in Section 8.1.1.2 Random Survival Forests, and will consider the potential predictive factors seen in Figure 2 in Section 8.2.3. In the event of missing data, see Section 7.3.

DAS28-4 CRP at Month 3 as a Potential Predictive Factor

8.2.5 As part of the sensitivity analyses, DAS28-4 CRP at month 3 will be considered as an additional potential predictive factor along with the factors seen in Figure 2 in Section 8.2.3, and will follow the methods described in Section Analysis of 8.1.1.1 Cox Proportional Hazards. This will use the Month 3 Analysis Set. In the event of missing data, follow Section 7.1.

The methods for random survival forests, described in Section 8.1.1.2 Random Survival Forests, will also be repeated including DAS28-4 CRP at month 3 as a potential predictive factor, along with the factors in Figure 2 in Section 8.2.3. This will use the Month 3 Analysis Set. In the event of missing data, follow Section 7.3.

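### SAP Table 8 adds DAS28-4 CRP at baseline to the Month 3 Cox sensitivity analysis, where the rest of the SAP specifies DAS28-4 CRP at month 3

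*SAP*

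**What the plan says.** Section 5.3 of the SAP defines the Month 3 Analysis Set and gives its purpose: "The sensitivity analyses where DAS28-4 CRP measured at month 3 is included as a potential factor will use the Month 3 analysis set".

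Section 8.2.4 has a block on DAS28-4 CRP at month 3. For the Cox model it says: "As part of the sensitivity analyses, DAS28-4 CRP at month 3 will be considered as an additional potential predictive factor", alongside the Figure 2 factors. For the random survival forest it says that the methods "will also be repeated including DAS28-4 CRP at month 3 as a potential predictive factor". Both are assigned to the Month 3 Analysis Set.

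Table 8 in Section 8.2.9 has two rows for this set. The Cox row specifies univariate selection followed by "backwards selection on the variables in Figure 2 and Das28-4 CRP at Baseline", so the covariate it adds is "Das28-4 CRP at Baseline". The next row, for the forest, specifies "Variables in Figure 2 and DAS28-4 CRP at Month 3, following the methods seen in Section" 8.1.1.2.

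**The concern.** The covariate that defines this Cox analysis differs between the methods text and the table that summarises it. I found no rule in the SAP on whether text or table prevails, and Section 9 places the table shells in a separate document, so the documents do not show which specification the programming will follow.

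If Table 8 is followed, the Cox model loses the one variable it was set up to examine. It becomes a selection among baseline factors, run on patients chosen because they have month-3 data. The Cox and forest analyses on that set would then examine different candidate factors, although Section 8.2.4 sets them up with the same added factor. If the conflict is found only after the data are seen, the choice of covariate can no longer be shown to have been made in advance.

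**Working it through.** No sample size, power figure or event count enters this point, so the check is a comparison of texts.

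**Step 1. Set the specifications side by side.**

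| Place in SAP | Analysis on the Month 3 Analysis Set | DAS28-4 CRP taken at |
|---|---|---|
| 5.3, purpose of the set | Sensitivity analyses in general | Month 3 |
| 8.2.4, text | Cox | Month 3 |
| 8.2.4, text | Random survival forest | Month 3 |
| 8.2.9, Table 8 | Cox | **Baseline** |
| 8.2.9, Table 8 | Random survival forest | Month 3 |

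Four of the five entries say month 3. The exception is the Table 8 Cox row.

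**Step 2. Confirm that the rows describe the same analysis.** The Table 8 Cox row and the Cox paragraph in 8.2.4 share the outcome (time to discontinuation), the analysis set, the model, the selection procedure and the missing-data method (missing data indicators). They differ only in the time point of the added covariate.

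**Step 3. Ask whether the month-3 score could enter by another route.** The row offers Figure 2 plus one added factor. Section 8.2.3 notes that the Figure 2 factors are all baseline predictors, so Figure 2 cannot supply it. The figure itself is not shown in the text available, which leaves two cases:

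- Baseline DAS28-4 CRP is already in Figure 2. The row then adds nothing to the primary factor list, and the run repeats the primary selection in a subset.
- Baseline DAS28-4 CRP is not in Figure 2. The row then adds one further baseline factor.

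In both cases the Cox model contains no month-3 variable.

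**Step 4. Compare the outputs.** Section 8.1.1.1 has the Cox models report hazard ratios, 95% confidence intervals and p-values. Section 8.1.1.2 has the forest report variable importance, an ensemble cumulative hazard estimate and an error rate. Under Table 8 the month-3 score would get the second kind of output and none of the first.

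**The case against.** The strongest reply is that this is a slip in a summary table. Section 8.2.4 is the operative methods section and it is unambiguous. The name and purpose of the analysis set make little sense with a baseline covariate, and the adjacent row is right. A programmer working from 8.2.4 would fit the intended model. This stands as far as intent goes: month 3 is clearly meant. It does not remove the contradiction, because Table 8 is current specification text that states covariates row by row.

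Three stronger readings are tempting, and the documents do not support them.

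- *Month-3 disease activity is never examined if Table 8 is followed.* The forest row of the same table includes it. Only the Cox estimate and test are lost.
- *Month-3 treatment response goes untested.* The variable is a disease activity score. Response is a separate EULAR category, defined in Section 6.1.1.2.10, and is not the factor added here.
- *Section 5.3 is itself an error that must be changed.* The set admits patients "who have at least one non-missing month 3 measurement", which need not be DAS28-4 CRP, so some members might lack the score. That wording is ambiguous, but the next sentence of 5.3 ties the set to DAS28-4 CRP. Handling of missing values is also pre-specified: indicators in the final multivariate Cox model (7.1, 8.2.3) and imputation in the forest (7.3). Requiring a non-missing score would replace this with a complete-case restriction on that factor, which is a debatable choice and not a correction. The documents give neither the size of the set nor the rate of missing month-3 scores, so no number of affected patients can be stated.

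**Conclusion.** The contradiction is certain and rests on the wording alone. The Table 8 Cox row for the Month 3 Analysis Set names the wrong time point, judged against Sections 5.3 and 8.2.4 and the adjacent forest row. Followed literally, it yields a Cox sensitivity analysis of baseline factors only, with no hazard ratio, confidence interval or p-value for month-3 DAS28-4 CRP.

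The reach is limited. One sensitivity analysis is affected. The primary Cox analysis, the forest on the same set and the behavioural-strategy models keep their specifications. The consequence arises only if the table is followed instead of the text. Whether the row duplicates the primary factor list or adds one baseline factor depends on Figure 2, which could not be seen; the conclusion is the same either way.

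**What to change.** In SAP Section 8.2.9, change the covariate entry of the Table 8 Cox row for the Month 3 Analysis Set from DAS28-4 CRP at baseline to DAS28-4 CRP at month 3. Check that the separate table shells carry the same time point.

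Optionally, ask the sponsor to state whether the month-3 measurement required in Section 5.3 means DAS28-4 CRP or any month-3 assessment. This is a request for clarification, not a required change to the set.

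The cost is one word in the SAP, made before the final analysis. It needs no new data and leaves the sample size alone. Protocol Section 9.7 reserves amendments for major changes to the primary endpoint or its analysis, so no protocol amendment is called for.

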9 LIST OF TABLES AND TABLE SHELLS

To be presented in a separate document.

11 APPENDICES

11.1 APPENDIX 1: DATA DERIVATION DETAILS

Table 9 Study Visits and Visit Windowing

Visit	Target Date	Target Day	Visit Window
Visit 0	Inclusion	1	Day 1 or before
Visit 1	1 month	30	Day 2 to Day 61
Visit 2	3 months	91	Day 62 to Day 137
Visit 3	6 months	183	Day 138 to Day 274
Visit 4	12 months	365	Day 275 to Day 457
Visit 5	18 months	548	Day 458 to Day 639
Visit 6	24 months	731	Day 640 onwards

In case of multiple observations falling within a given window, the observations selected for analysis will be identified as follows:

1. The observation closest to the target day will be used.
2. If the observations are at equal distance from the target day in absolute value, the one with a correct nominal visit label will be used.
3. If neither (1) nor (2) can be used to identify the observation windowing, then the latest observation within the analysis window will be used.
